### **Side effects:**

The following side effects, as well as their frequency, have been observed in SUNITINIB clinical studies:

- **Likely (50% or more):** fatigue.
- **Frequent (10-50%):** diarrhea, nausea, upset stomach, taste disturbances, stomatitis/mucositis, vomiting, constipation, yellowing of the skin, anorexia, arthralgia and myalgia, hypertension, dermatitis, headache, blisters and/or rash in hands and feet which may be painful, increased lipase and amylase, hair color changes, shortness of breath, edema, dehydration.
- **Occasional (1-10%):** nosebleeds, leucopenia/neutropenia, anemia, thrombocytopenia, insomnia, cough, fever, increased/more frequent eye tearing, alopecia, increase creatinine, increased LFTs, reduced ejection fraction, increased cardiac enzymes.
- **Rare (less than 1%):** bleeding requiring transfusion (including bleeding into the tumor), thrombosis, infection, hypoadrenalinism, increased TSH, hypothyroidism, decreased blood flow to the brain, pancreatitis, myocardial infarction, bowel perforation/intestinal fistulae, pneumothorax, seizure, temporary loss of vision. One patient developed thrombosis of the portal vein.

### **Procedure for Handling Drug Spills**

Following direct contact with skin, the contents of the capsules may cause yellow discoloration of the exposed area. The exposed area should be washed with soap and water immediately.

### **OVERDOSAGE**

## [name], Phase II Study of BCG followed by Sunitinib for High risk NMIBC

No overdose of SUNITINIB was reported in completed clinical studies. In non-clinical studies mortality was observed following as few as 5 daily doses of 500 mg/kg (3000 mg/m^2) in rats. At this dose, signs of toxicity included impaired muscle coordination, head shakes, hypoactivity, ocular discharge, piloerection and gastrointestinal distress. Mortality and similar signs of toxicity were observed at lower doses when administered for longer durations. Treatment of overdose with SUNITINIB should consist of general supportive measures. There is no specific antidote for overdosage with SUNITINIB. If indicated, elimination of unabsorbed drug should be achieved by emesis or gastric lavage.

### **Drug Storage**

Since SUNITINIB may be light sensitive, the capsules will be stored in the bottles in which they are received to protect the compound from light. Bottles containing SUNITINIB capsules must be stored at controlled room temperature (15-30°C).

### **Compliance**

Patients will be required to return all bottles of study medication at the beginning of each cycle. The number of capsules remaining will be documented and recorded.

#### *11.2.1 AGENT ORDERING*

Sunitinib may be requested by the principal investigator (or their authorized designees). See Appendix E for drug request forms.

#### *11.2.2 AGENT ACCOUNTABILITY*

The investigator, or an approved representative, e.g. pharmacist, will ensure that all investigational products are stored in a secured area, under recommended storage conditions and in accordance with applicable regulatory requirements. All study drug supplies must be kept in a locked limited access room. The study drug must not be used outside the context of the protocol. Under no circumstances should the investigator or other site personnel supply study drug to other investigators, patients, or clinics, or allow supplies to be used other than directed by this protocol. The investigator must maintain adequate records documenting the receipt, use, loss or other deposition of the investigational product, including batch or code numbers, and account for its disposition on patient-by-patient basis, including specific dates and quantities. The prescribed dose should also be recorded in the patient's medical records.

Destruction must be adequately documented.

## **12.0 CORRELATIVE STUDIES:**

Evaluation of biomarkers in tissue, urine, and serum

Serum levels of biomarkers of the vascular endothelial growth factor receptor (VEGF-R) pathway including VEGF and soluble VEGFR-2 (sVEGFR-2) have been serially measured in a Phase I [29] as

## [name], Phase II Study of BCG followed by Sunitinib for High risk NMIBC

well as a phase II [30] study of SUNITINIB in patients with renal cell cancer. In these studies, VEGF was found to be increased and sVEGF-R2 levels decreased by the end of each dosing cycle (day 28). After two weeks off therapy, levels returned to near baseline (day 1). Differences in day 1 and day 28 levels were statistically significant. In addition, in patients with metastatic renal cell carcinoma, when mean marker level changes were correlated with tumor response, larger proportional changes in VEGF and sVEGFR-2 levels were observed in patients exhibiting objective responses compared with those exhibiting stable or progressive disease [31].

As described above, VEGF inhibition is likely important in BCG's effect on bladder cancer. VEGF receptors are present in the normal urothelium and are also upregulated during inflammation such as that occurring in interstitial cystitis. BCG is known to cause bladder inflammation and therefore may cause upregulation of VEGFR receptors in normal as well as malignant bladder cells.[27] Thus the combination of BCG followed by sunitinib may sensitize bladder tumors to response to BCG by blocking the VEGF receptor pathway. Alternatively, tumor cells not affected by BCG may be targeted by sunitinib thus providing an opportunity to consolidate complete response to therapy.

Additionally, other tissue markers may provide important information for patient stratification. For example, p53 mutation, which is common even in non-muscle invasive bladder cancer [32], may also be involved in regulated angiogenesis and response to hypoxia [33] Thus, the p53 status of patients may alter responses to sunitinib. Another important tissue marker is HIF1a, a marker upregulated with tissue hypoxia. Elevated tissue levels of HIF1a may indicate activation of the VEGF pathway, and thus indicate patients who would be more likely to respond to treatment [35] Each of these additional hypotheses can be tested using formalin-fixed, paraffin-embedded tissues subjected to immunoperoxidase staining after antigen retrieval [ 34].

Urine represents an ideal medium to evaluate response to therapy in patients with localized bladder cancer as it may directly indicate the response to therapy. Further, based on preliminary results described previously, serum levels of biomarkers may also be informative. We will investigate the effect of BCG and sunitinib therapy on urinary and serum levels of various VEGFs, soluble VEGF receptors, and cytokines IL8, IL6, interferon gamma, and interferon alpha. Measurements will be performed using commercially-available ELISA kits. Utility of additional biomarkers (e.g., PDGF, [35]) will be evaluated on a pilot basis.

Correlation of changes in VEGF, VEGFR, p53, and other cytokine expression to response will be explored. Markers will be grouped based on terciles of the distribution. Bivariate relationships between the expression level and response status will be assessed with the Mantel-Haenszel chi-square test. Logistic regression will be used to assess the effect of combining markers to predict response. Differences in time to recurrence by expression level will be illustrated by Kaplan-Meier plots and tested using the log-rank test. Due to the sample size and the number of factors we will be statistically testing, these analyses will be considered exploratory until confirmed in a larger, independent, clinical trial.

### **Procedures and Methods:**

## [name], Phase II Study of BCG followed by Sunitinib for High risk NMIBC

- Voided urine and serum will be obtained as outlined on the study calendar. If BCG is given locally no specimens need to be obtained at Week 1 and Week 6 visits. In addition, a bladder biopsy will be obtained at the 3 month endoscopic biopsy to assess response. These specimens will only be obtained for the first study cycle.
- Urine will be kept on ice until it can be centrifuged in the research laboratory. The urine and pellet will aliquoted into separate tubes, codes, and stores at -80°C in the research laboratory.
- Tissue will be collected at the time of bladder biopsy at 3 months and processed with formalin fixation and paraffin-embedding in the Pathology Department, following the standard operating procedure of the previously approved University of Michigan Bladder Cancer (Tissue/Blood/Urine/Data) Bank (IRB 1996-0379). Blocks and tissue sections will be stored in research lab until processed.
- Tissue biomarker standardization will be performed by microscopic evaluation in collaboration with a pathologist. Each assay will be performed with positive and negative control tissues from comparisons. Responses will be scored based on the number of cells staining positive and the level of positivity (0-3+).
- Urine biomarker standardization will be based on urine creatinine measurements.

## 13.0 STUDY CALENDAR:

[name], Phase II Study of BCG followed by Sunitinib for High risk NMIBC

		Week 1-6 BCG Course 1		Week 8-12† Sunitinib cycle 1			TURBT or bladder biopsy	Therapeutic Plan			
Required studies	Pre-study	Week1	Week 6	Week 8	Week 10	Week 12	Week 14	1. Residual/Recurrent disease without progression: a. Negative MUGA scan-if positive, proceed to 3. b. 2 nd cycle of BCG followed by sunitinib (as per week 1-14) c. alternative treatment plan per treating clinician 2. No residual disease (Calendar 2): patient will proceed to maintenance BCG therapy per institutional standard a. alternative therapy may be chosen on maintenance at patient/physician discretion 3. Disease progression or patient/clinician desire: proceed to alternative treatment per standard of care			
PHYSICAL											
History and Physical	x			x	x	x					
ECOG performance status	x			x	x	x					
Medication check	x			x	x	x					
Toxicity assessment											
LABORATORY/ STUDIES											
CBCPD	x			x	x	x					
Comprehensive panel	x			x		x					
Magnesium				x		x					
EKG	x										
Dipstick Urine		x	x								
Urine cytology*	x						x				
PT/PTT	x					x					
TSH	x										
MUGA Scan	x										
SPECIMEN SAMPLES											
Urine*		x 	x 	x		x	x				
Bladder biopsy							x				
Serum		x 	x 	x		x					
X-RAYS AND SCANS											
Chest radiograph	x										
CT or MRI abdomen/ pelvis or IVP	x										
Cystoscopy or report confirming eligibility	x										
Drug: Sunitinib				x							
Dispense BP log, Study drug info, and medication diary				x							

\* voided urine cytology obtained in clinic, instrument urine cytology obtained in operating room

† Medical Oncologist will prescribe sunitinib and monitor for toxicity during treatment

 If BCG is given locally no specimens need to be obtained at the Week 1 and Week 6 visits.

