## [name], Phase II Study of BCG followed by Sunitinib for High risk NMIBC

4.2.2 Comprehensive panel: sodium, potassium, chloride, bicarbonate, BUN, creatinine, glucose, calcium, AST, ALT, alkaline phosphatase, bilirubin, total protein and albumin.

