# if BCG infection of grade 3 or 4 occurs during the 1st induction course, patients will be withdrawn from the study and replaced. Otherwise, patients will be offered alternative therapy at the discretion of the treating clinician and followed for appropriate endpoints.

### 10.2 SUNITINIB: In the event of any (CTC version 3) drug related grade 3 or 4 non-hematologic or

Toxicity	Grade 1	Grade 2	Grade 3	Grade 4
Irritative Bladder symptoms	Continue at the same dose level	Continue at the same dose level.	Dose reduction to -1. If Grade 3 toxicity persists, reduction to -2. Discontinuation will occur at the discretion of the treating clinician.	Dose reduction to -1. If Grade 4 toxicity persists, reduction to -2. Discontinuation will occur at the discretion of the treating clinician.
Fever, chills and "flu-like" symptoms	Continue at same dose level.	Continue at same dose level.	Dose reduction to -1. If Grade 3 toxicity persists, reduction to -2. Discontinuation will occur at the discretion of the treating clinician	Dose reduction to -1. If Grade 4 toxicity persists, reduction to -2. Discontinuation will occur at the discretion of the treating clinician
Occular symptoms +/- joint symptoms	Continue at the same dose level.	Continue at the same dose level.	Dose reduction to -1. If Grade 3 toxicity persists, reduction to -2. Discontinuation will occur at the discretion of the treating clinician	Dose reduction to -1. If Grade 4 toxicity persists, reduction to -2. Discontinuation will occur at the discretion of the treating clinician
Infection	Treat* and continue at same dose after resolution of symptoms within 2 weeks	Treat* and continue at same dose after resolution of infection within 2 weeks	Withdraw BCG treatment#	Withdraw BCG treatment#

grade 4 hematologic adverse event(s) drug should be held until the toxicity resolves to < grade 1 and then the drug should be restarted at -1 dose level (see 6.1).

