#### 10.2.1 DOSE REDUCTION FOR SUNITINIB

- Intrapatient dose reduction by 1, and if needed 2- dose level(s) will be allowed (see 6.1) depending on the type and severity of toxicity encountered provided that criteria for patient withdrawal from study treatment have not been met.
- All intra-patient dose reductions are relative to the lowest dose level of the current cycle.
- Recovery to acceptable levels of toxicity must occur within 4 weeks to allow continuation in the study.

[name], Phase II Study of BCG followed by Sunitinib for High risk NMIBC

- No more than 2 dose reductions are permitted in any patient. If further dose reductions are required, patients will discontinue sunitinib therapy. They will continue to be followed per protocol.
- The following table describes the recommended dose modifications for study treatment associated toxicity.

TABLE: DOSE MODIFICATION OF SUNITINIB BASED ON TOXICITY AND GRADE

Recurring grade 3 toxicity requires dose reduction \* Patients who develop grade 3 or 4 hyperlipasemia or hyperamylasemia without clinical or other evidence of pancreatitis, or grade 4 hyperuricemia or grade 3 hypophosphatemia without clinical symptoms may continue study treatment without interruption. \*\*\* Patients with recurrent grade 3 lymphopenia and anemia do not require dose modification. Recurring grade 4 neutropenia or grade  $\geq 3$ thrombocytopenia persisting for at least 5 days requires dose reduction in the next cycle. Grade 4 lymphopenia does not require dose reduction.

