**Management of cardiac ejection fraction.**

Toxicity	Grade 1	Grade 2	Grade 3	Grade 4
Non-hematologic	Continue at the same dose level	Continue at the same dose level.	Withhold dose until toxicity is grade $\leq 1$ , or has returned to baseline, then resume treatment at the same dose level or reduce the dose by 1 level at the discretion of the investigator*.	Withhold dose until toxicity is grade $\leq 1$ , or has returned to baseline, then reduce the dose by 1 level and resume treatment, or discontinue at the discretion of the investigator*.
cardiac toxicity:	Continue at the same dose level.	Continue at the same dose level except in the event of Non-urgent ventricular paroxysmal dysrhythmia requiring intervention, Withhold dose until toxicity is grade $\leq 1$ , then reduce dose by 1 level and resume treatment.	Remove from further therapy, follow for applicable endpoints	Remove from further therapy, follow for applicable endpoints
Neurotoxicity	Continue at the same dose level.	Withhold dose until toxicity is grade $\leq 1$ , then continue at same dose level.	Withhold dose until toxicity is grade $\leq 1$ , then reduce the dose by 1 level and resume treatment.	Remove from further therapy, follow for applicable endpoints
Fever, chills and "flu-like" symptoms	Continue at same dose level.	Continue at same dose level.	Withhold dose until toxicity is grade $\leq 2$ , or has returned to baseline, then resume treatment at the same dose level.	Withhold dose until toxicity is grade $\leq 2$ , then reduce the dose by 1 level and resume treatment.
Hematologic	Continue at the same dose level.	Continue at the same dose level.	Withhold dose until toxicity is grade $\leq 2$ , or has returned to baseline, then resume treatment at the same dose***.	Withhold dose until toxicity is grade $\leq 2$ , then reduce the dose by 1 level and resume treatment***.

All patients will undergo a MUGA scan prior to enrollment in the study. Patients proceeding to a second cycle of therapy (BCG followed by sunitinib) will undergo a MUGA scan prior to initiation of the second cycle. Patients with an ejection fraction lower than the institutional lower limit of normal will not receive further study treatment per protocol and will be offered alternative therapy as directed by the treating clinician.

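### Calendar 1 has no chemistry panel at Week 10, so for a course given on schedule the sunitinib hold rule has no scheduled mid-course input for silent renal or hepatic abnormalities

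*Combined protocol and SAP*

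**What the plan says.** - **Schedule.** In Calendar 1 (13.0) the chemistry row, "Comprehensive panel", is marked at Pre-study, Week 8 and Week 12. The CBC row is marked at those visits and also at Week 10, as are history and physical, performance status and the medication check. No other section schedules chemistry during sunitinib dosing.
- **Panel content (4.2.2).** "Comprehensive panel: sodium, potassium, chloride, bicarbonate, BUN, creatinine, glucose, calcium, AST, ALT, alkaline phosphatase, bilirubin", together with total protein and albumin.
- **Hold rule.** For a drug-related grade 3-4 non-hematologic event, section 10.2 says "drug should be held until the toxicity resolves to < grade 1". The dose-modification table in 10.2.1 also withholds at grade 3, "then resume treatment at the same dose level or reduce the dose by 1 level at the discretion of the investigator". The two differ on the restart dose but agree on the hold.
- **Laboratory exemptions (10.2.1).** Raised lipase or amylase without pancreatitis is exempt. So are patients with "grade 4 hyperuricemia or grade 3 hypophosphatemia without clinical symptoms may continue study treatment without interruption". Creatinine, AST/ALT and bilirubin are not on the list.
- **Expected effects (11.2).** The 1-10% group for sunitinib includes "increase creatinine, increased LFTs, reduced ejection fraction", with no grade given.
- **General safeguard (13.0, footnote †).** "Medical Oncologist will prescribe sunitinib and monitor for toxicity during treatment". No test or date is named.
- **Second course (13.0, Therapeutic Plan 1b).** A "cycle of BCG followed by sunitinib (as per week 1-14"), so it follows the same schedule.

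**The concern.** The hold rule covers laboratory abnormalities that a patient may not feel, but the tests that would show them are scheduled only when drug is dispensed and when dosing is nominally over. The Week 8 panel comes before or with the first dose, so it cannot show a sunitinib effect. The Week 12 panel can guide recovery, toxicity reporting and a second course, but on a course given on schedule it comes too late to spare more than a few doses. The Week 10 history and physical can pick up clinical toxicity but not a silent rise in creatinine, transaminases or bilirubin.

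What is at stake is patient safety on a small scale: some patients could keep taking sunitinib past a point at which the protocol's own rule would have stopped it.

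**Working it through.** The plan states no figure to reproduce here. The check is a reading of the calendar followed by a day count.

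**1. Is the blank real?** The magnesium and research-serum rows also skip Week 10, while the CBC, history, performance status and medication rows do not. That consistent pattern makes a misplaced mark unlikely. One caution is that the toxicity-assessment row in Calendar 1 has no marks at all, whereas its counterpart in Calendar 2 does.

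**2. Doses left at each visit.** Inputs: 28 daily doses (Protocol Summary, Schedule); dispensing at Week 8 (Calendar 1); sunitinib starts two weeks after BCG (7.2). With first dose on day s and visit on day v, and counting the visit day's dose as still avoidable:

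doses remaining = s + 28 − v, bounded by 0 and 28.

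*Nominal reading*: Week 8 visit = day 0, Week 10 = day 14, Week 12 = day 28.

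| First dose | Left at Week 10 | Left at Week 12 |
|---|---|---|
| Day 0 | 0 + 28 − 14 = 14 (50%) | 0 + 28 − 28 = 0 |
| Day 1 | 1 + 28 − 14 = 15 (54%) | 1 + 28 − 28 = 1 (4%) |

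*Widest visit-day reading*: each visit on any day of its calendar week, where Week k covers days 7(k−1) to 7k−1. Week 8 is then days 49-55, Week 10 days 63-69 and Week 12 days 77-83. The first dose is on the dispensing day or the next day, so s runs from 49 to 56.

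- Week 10: from 49 + 28 − 69 = 8 (29%) to 56 + 28 − 63 = 21 (75%).
- Week 12: from 49 + 28 − 83 = −6, that is 0, to 56 + 28 − 77 = 7 (25%).

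If the two-week rest runs from the end of Week 6, the first dose is on day 56. That leaves 15-21 at Week 10 and 1-7 at Week 12, inside the same range.

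*Late or interrupted dosing*: with visits kept to the calendar, each day that dosing slips adds one dose to the number left at Week 12. For an interruption this assumes that held doses are made up, which the documents do not say.

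**3. How many patients could be concerned?** The only rate in the documents is 1-10%, grade not stated (11.2). Under 16.1 every evaluable patient has received sunitinib.

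- 36 patients: 36 × 0.01 = 0.36 to 36 × 0.10 = 3.6 per abnormality.
- First 24 patients: 24 × 0.01 = 0.24 to 24 × 0.10 = 2.4.

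If the rate here is no higher than in the sunitinib studies, these are ceilings for grade 3-4. They are not estimates of it.

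**The case against.** The strongest reply is that this is a deliberate and defensible schedule: chemistry at the start and end of a single 28-day course, with a clinical and blood-count check in the middle. No rule in the protocol requires mid-course chemistry, so there is no contradiction between sections. The calendar is also not the limit of testing. The oncologist must monitor for toxicity, and the investigator may suspend dosing (11.2). The exemptions in 10.2.1 concern lipase, amylase, uric acid and phosphate, none of which is in the panel or any calendar row, so the dose rules already presuppose clinician-ordered tests. Entry limits (3.1.8) and the Week 8 panel screen out pre-existing dysfunction.

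Much of this stands. It shows that the gap is small and that the blank should not be called a mistake. It does not supply a scheduled result: neither the monitoring duty nor the power to suspend names a test, and a silent abnormality gives no prompt to order one.

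A reader might also infer three stronger things that the documents do not support:

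- **That an unscheduled test is the only way to trigger a useful hold.** Up to 7 doses can remain at the scheduled Week 12 panel, and more if dosing runs late or is interrupted.
- **That a Week 10 panel would spare 14-15 doses.** It could do so only for a patient already at grade 3-4 by that visit. Onset timing is not given, and an abnormality arising after Week 10 would still be missed.
- **That 1-10% of patients would meet the hold threshold.** That figure has no grade, and the true grade 3-4 count could be close to zero.

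**Conclusion.** The point holds as a modest safety improvement. For a course given on schedule, the hold rule has no scheduled mid-course input for silent creatinine, AST/ALT or bilirubin abnormalities, and timely detection rests mainly on an unscheduled test. The size of the gap is the difference in doses still to be given: 14-15 of 28 at Week 10 against 0-1 at Week 12 nominally, or 8-21 against 0-7 on the widest visit-day reading.

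This rests on the Week 10 blank being as printed and on dosing that starts at or about Week 8 and runs without interruption. How often the gap would matter cannot be calculated from the documents. The primary endpoint, sample size and analyses are unaffected, and the point is no reason to delay the trial.

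**What to change.** Add a mark for the comprehensive panel at Week 10 in Calendar 1, to be run on the blood already drawn for the CBC. A second course inherits the mark through its reference back to the first-course schedule, so no further text is needed. The cost is one extra chemistry assay per course, with no new visit, procedure or staff.
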